[⁶⁸Ga]DOTATATE (tradename NETSPOT) is a peptide-based radiopharmaceutical for positron emission tomography (PET) that was approved for clinical use in the United States in 2016 for the evaluation of somatostatin receptor (SSTR)-positive neuroendocrine tumors (NETs). This PET tracer binds to SSTRs on the surface of tumor cells with the highest affinity for the SSTR2 receptor which is overexpressed in neuroendocrine tumors. In patients with metastatic NETs, somatostatin analogues (e.g. octreotide and lantreotide) are a mainstay in control of symptoms, but do not treat the underlying metastatic disease. In 2018, the FDA approved a therapeutic analogue of DOTATATE ([¹⁷⁷Lu]DOTATATE, tradename Lutathera) for the treatment of SSTR-positive gastroenteropancreatic NETs. A key concept is that [⁶⁸Ga]DOTATATE-PET is used to evaluate metastatic NETs for SSTR expression and use this information to select potential candidates for [¹⁷⁷Lu]DOTATATE therapy. This theranostic approach can potentially be applied to other tumors that express adequate levels of SSTR.

SSTR expression has previously been demonstrated in the setting of HCC to varying degrees. A study of 53 resected HCCs demonstrated that membrane SSTR2 was reliably detected in HCC and could serve as a potential therapeutic target.[4] Multiple tissue-based studies demonstrate SSTR positivity in 20-50% of HCCs.[4-6] Additionally, SSTR2 expression in HCC was positively correlated with cytokeratin 19-9 expression, serum alpha-fetoprotein level, and poor differentiation, all of which are poor prognostic markers for patients with HCC.[4, 7, 8] Additional studies have confirmed SSTR expression in HCC with varying distributions of the SSTR receptor subtype expression.[5, 6] However, the fraction of HCCs have high enough levels of SSTR for [¹⁷⁷Lu]DOTATATE therapy has not yet been assessed. Therefore, it is our aim to use [⁶⁸Ga]DOTATATE-PET/MRI to assess tumor SSTR expression in patients with HCC before and after locoregional therapy. This research plan is a critical prerequisite for determining the feasibility of this theranostic approach to treating HCC. If we obtain positive results, these data will be critical for designing a combined imaging and therapeutic study in HCC using DOTATATE.

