4.6.4 PET/CT and PET/MRI Imaging Interpretation and Storage

Images from the PET/CT and PET/MRI will be anonymized and subsequently stored and reviewed using a commercially available software package (MIM Encore, Cleveland, OH). The PET and whole body MRI studies will not be available in the UAB PACS system. This is in an effort to blind the treating physicians from making clinical decisions on an experimental imaging technique. The liver MRI images will be sent to clinical PACS and the medical record as part

of standard-of-care imaging and can be used in the clinical-decision making process. No formal interpretation will be generated for the [⁶⁸Ga]DOTATATE-PET or whole body MRI portion of the study.

PET/CT and PET/MRI images will be interpreted by board certified physicians specialized in molecular imaging and abdominal imaging. Images will initially be interpreted as positive or negative for SSTR-positive HCC. HCC lesions will be considered SSTR positive for the purposes of this study if they have higher [⁶⁸Ga]DOTATATE activity than adjacent liver not involved by HCC. The amount of [⁶⁸Ga]DOTATATE binding for intrahepatic HCCs will be further characterized based on visual analysis as less than skeletal muscle (no binding), higher than skeletal muscle but less than or equal to adjacent liver (low binding), higher than adjacent liver but less than spleen (moderate binding) or equal to or greater than spleen (high binding). For patients with SSTR-positive HCC and positive [⁶⁸Ga]DOTATATE PET, intrahepatic and extrahepatic disease will be assessed on MRI/CT alone first, with confidence in interpretation rated on a 1-5 scale (1 = negative, 5 definite). Following this, fused PET/CT or PET/MRI images will be assessed and rated on the same 1-5 scale.

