6.2 Sample Size Justification

As this is a pilot feasibility study, no formal hypothesis will be testing, and thus no power analysis was performed. The primary objective is to determine the frequency of somatostatin receptor positivity in hepatocellular carcinoma using [⁶⁸Ga]DOTATATE-PET. In this study, patients with treatment-naïve HCC (n=15) and patients with previously treated HCC being referred for systemic chemotherapy and/or best supportive care (n=15) will be enrolled through the UAB Hepatobiliary Tumor Board in order to estimate the percentage of patients with moderate to high binding of [⁶⁸Ga]DOTATATE on PET examinations. Patients will undergo a single whole body [⁶⁸Ga]DOTATATE-PET/MRI or PET/CT to assess SSTR positivity of their HCCs. If a sufficient fraction (20% or greater) of HCC seen on conventional anatomic imaging demonstrate levels of somatostatin receptor expression to result in a positive DOTATATE PET scan, a subsequent therapeutic clinical trial with [¹⁷⁷Lu]DOTATATE will be carried out. With a total of 30 patients enrolled, the estimated percentage of positive binding of [⁶⁸Ga]DOTATATE will have two-sided 95% confidence intervals (CI) from $7.7\% \leq p \leq 38.6\%$ using the Clopper-Pearson (exact) method assuming at least 20% positive binding occurs. Although the confidence interval will be wide for each subgroup, e.g. treatment-naïve HCC or previously treated HCC with n=15 (95% CI $4.3\% \leq p \leq 48.1\%$), it will provide early evidence if the [⁶⁸Ga]DOTATATE binding will be affected by prior treatment and/or stage of disease.

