6.4 Statistical Analysis Plan

This study will largely be exploratory and descriptive. For all clinical and histological evaluations as well as imaging parameters, we will generate summary tabulations of the number of observations, mean, standard deviation, median, minimum, and maximum for continuous variables, and the frequency and percentage for categorical variables. Analyses will be primarily descriptive and graphical in nature. The count, and percentage of patients with HCCs showing activity in their HCC greater than liver and/or spleen will be estimated using Clopper-Pearson (exact) method along with two-sided 95% CI. The estimation will be provided for all 30 patients first, and then by treatment-naïve or not.

Concordance between [⁶⁸Ga]DOTATATE PET results and liver MRI results for patients with SSTR-positive HCC and positive [⁶⁸Ga]DOTATATE PET, intrahepatic and extrahepatic disease will be assessed on MRI/CT alone first, with confidence in interpretation rated on a 1-5 scale (1 = negative, 5 definite). Following this, fused PET/CT or PET/MRI images will be assessed and rated on the same 1-5 scale. Scale 3-4

is defined as positive. The agreement (concordance) between nominal (e.g. scale 1-5) or binary outcome (positive or negative) of [⁶⁸Ga]DOTATATE PET results and liver MRI results will be assessed using Cohen's kappa coefficients with one-side 95% confidence intervals. Based on values of Cohen's kappa, the agreement will be considered as poor (>0.2), fair (0.21-0.40), moderate (0.41-0.60), good (0.61-0.80), and very good (0.81-1.0) ([Dtsch Arztbl Int. Concordance Analysis. 2011 Jul; 108\(30\): 515-521. PMID: 21904584](#)). Bland-Altman diagrams will be used to evaluate agreement for other continuous imaging variables between these two methods. All statistical analysis will be carried on SAS v9.4.

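### Section 6.4 treats the ordered 1–5 confidence score as nominal, names no kappa weights, and prints the lowest agreement band with its inequality reversed

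*Combined protocol and SAP*

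**What the plan says.** Section 5.1 (Primary Endpoint) lists two items, and the second is concordance between the PET and liver MRI results.

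Section 4.6.4 says who is rated and how. The rating sentence opens "For patients with SSTR-positive HCC and positive" PET. Disease is read on MRI/CT alone and then on the fused images, each time "with confidence in interpretation rated on a 1-5 scale (1 = negative, 5 definite"). Section 6.4 repeats the same anchors.

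Section 6.4 then describes the data as "The agreement (concordance) between nominal (e.g. scale 1-5) or binary outcome (positive or negative") and says agreement "will be assessed using Cohen's kappa coefficients with one-side 95% confidence intervals". No weighting scheme is given there or elsewhere. The verbal scale follows: "the agreement will be considered as poor (>0.2), fair (0.21-0.40), moderate (0.41-0.60), good (0.61-0.80), and very good (0.81-1.0").

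**The concern.** There are two separate faults in one paragraph.

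**Scale type.** The anchors put the five scores in order. Calling the score nominal says that the order carries no information. Nominal data with plain Cohen's kappa means simple kappa, under which every disagreement counts the same. For a confidence rating that discards what a reader most wants to know: whether adding PET shifts the MRI/CT read by one step or overturns it. An analyst who notices the ordering once the data are in could turn to weighted kappa, and would then choose the weights with the results in view.

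**Bands.** The inequality on the lowest band points the wrong way. As printed, the band labelled poor contains all the bands above it, and low or zero agreement has no label.

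At stake are the statistic and the verbal label reported for an item listed as a primary endpoint.

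**Working it through.** **Plan's own figures.** The plan gives no figure for kappa. Its only precision figures are the exact intervals in Section 6.2. They reproduce: 6/30 gives 7.71% to 38.57% (printed 7.7% to 38.6%), and 3/15 gives 4.33% to 48.09% (printed 4.3% to 48.1%). The point made here does not depend on them.

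**Number of patients rated.** Section 6.2 works from "assuming at least 20% positive binding occurs": 30 × 0.20 = 6. Section 1.2 says "Multiple tissue-based studies demonstrate SSTR positivity in 20-50% of HCCs"; the top of that range gives 30 × 0.50 = 15. There may be more ratings if intrahepatic and extrahepatic disease are scored separately; the documents do not say.

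**Formulas.** Simple kappa = (po − pe)/(1 − pe). Weighted kappa = 1 − (observed mean disagreement)/(expected mean disagreement). For scores i and j on the full 1–5 scale, the disagreement is |i − j|/4 (linear) or (|i − j|/4)² (quadratic).

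**Illustration A: assumed data, six pairs (MRI/CT, fused).**

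- Near: (1,1) twice, (4,4), (5,5), (4,5), (5,4).
- Far: (1,1), (4,4) twice, (5,5), (1,5), (5,1).

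Both tables have margins 2/2/2 on scores 1/4/5, so po = 4/6 = 0.667, pe = 3 × (1/3)² = 0.333, and simple kappa = 0.333/0.667 = 0.50.

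- Linear expected disagreement: 2 × (3 + 4 + 1)/4/9 = 0.444.
- Quadratic expected disagreement: 2 × (9 + 16 + 1)/16/9 = 0.361.

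| | Simple | Linear | Quadratic |
|---|---|---|---|
| Near | 0.50 | 1 − 0.0833/0.444 = 0.81 | 1 − 0.0208/0.361 = 0.94 |
| Far | 0.50 | 1 − 0.333/0.444 = 0.25 | 1 − 0.333/0.361 = 0.08 |

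Simple kappa labels both tables moderate. Linear weights label them very good and fair.

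**Illustration B: same design, scores 3, 4 and 5 only.** Margins are again 2/2/2 with four exact agreements, so simple kappa is 0.50. Linear expected disagreement is 2 × (1 + 1 + 2)/4/9 = 0.222.

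- Two one-step discordances: observed 2 × 0.25/6 = 0.0833, linear kappa 1 − 0.0833/0.222 = 0.63.
- Two two-step discordances: observed 2 × 0.50/6 = 0.167, linear kappa 1 − 0.167/0.222 = 0.25.

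**Illustration C: scores 4 and 5 only.** With (4,4) twice, (4,5) twice and (5,5) twice, po = 0.667, pe = (4 × 2 + 2 × 4)/36 = 0.444, and kappa = 0.222/0.556 = 0.40. All three versions agree, because with two score levels every discordance has the same size.

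**Precision at simple kappa 0.50 (margins as in A).** SE = √[po(1 − po)/(n(1 − pe)²)].

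- n = 6: SE = √[0.222/(6 × 0.444)] = 0.289; one-sided 95% lower limit 0.50 − 1.645 × 0.289 = 0.025.
- n = 15: SE = 0.183; lower limit 0.50 − 1.645 × 0.183 = 0.20.

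**Bands as printed.** A kappa of 0.50 satisfies both the poor and the moderate rule; a kappa of 0.20 or below satisfies none. That range can be reached. If all six fused reads are 5 and the MRI/CT reads are 4, 4, 5, 5, 5, 5, then po = 4/6, pe = (4 × 6)/36 = 4/6, and every version of kappa is 0.00. If the lowest band is read as 0.20 or less, every kappa to two decimals gets exactly one label.

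**The case against.** The strongest reply is that nothing is left open. Nominal data with Cohen's kappa is a definite choice, it can be computed, and weighting adds an arbitrary choice between linear and quadratic. That stands in part: the plan can be carried out as written. But the choice contradicts the plan's own anchors and discards the size of each disagreement. Naming the weights in advance also settles the arbitrary element.

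A second reply is that scores of 1 are unlikely for intrahepatic disease, since eligibility (Section 3.3) requires viable tumour on MRI or CT and only PET-positive patients are rated. This is a fair limit on illustration A, which suits extrahepatic disease better. Illustration B meets it: with scores 3 to 5 only, the same simple kappa of 0.50 becomes 0.63 or 0.25. If scores fall on two levels only, the objection is right and weighting changes nothing.

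Third, sampling error is larger than the weighting effect. At n = 6 the one-sided margin is 1.645 × 0.289 = 0.475, against shifts of +0.31 and −0.25 (linear) or +0.44 and −0.42 (quadratic). That stands, and it limits the practical harm.

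Fourth, the band is an obvious misprint that few readers would apply literally. This is agreed, and alone it would be an erratum. The zero-kappa example comes from rating only PET-positive patients and would not be cured by weighting; it bears only on the band.

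Finally, the study is descriptive, with no formal test, and the decision on a therapeutic trial uses the 20% positivity threshold. That also stands.

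**Conclusion.** The concern holds. The plan calls an ordered score nominal, names no weights, and prints a lowest band that is wrong on the evidence of the next band, which starts at 0.21. The choice of weights can move the reported label by one or two bands when three or more score levels occur, and by nothing when only two occur.

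The impact is modest: roughly 6 to 15 rated patients, a kappa imprecise under any weighting, and no decision tied to it. A correction is still worth making because concordance is listed under Section 5.1 and Section 6.4 turns kappa into a verbal conclusion.

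The size rests on assumed tables, not expected results. The figure of 6 rests on the plan's 20% assumption. The figure of 15 treats tissue positivity as if it were PET uptake above liver, which the documents do not claim.

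**What to change.** In Section 6.4:

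1. Call the 1–5 score ordinal and pre-specify weighted kappa for it, stating the weights (for example linear). Report simple kappa beside it.
2. Keep simple kappa for the binary outcome, and state where score 5 falls. The positive range is printed as 3 to 4, so the binary kappa cannot be computed until score 5 is placed.
3. Print the lowest band as poor (≤0.20).
4. Show the paired 1–5 table and the number of rated patients beside each kappa, so that a small-sample value can be judged directly.

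The cost is SAP wording only. Weighted kappa uses the same ratings and the SAS v9.4 software already named.

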6.5 Data and Safety Monitoring Plan

6.5.1 Pre-Study Documentation

This study will be conducted in accordance with the ethical principles that have their origin in the Declaration of Helsinki as stated in 21 CFR §312.120(c)(4); consistent with GCP and all applicable regulatory requirements.

Before initiating this trial, the Investigator will have written and dated approval from the Institutional Review Board for the protocol, written informed consent form, subject recruitment materials, and any other written information to be provided to subjects before any protocol related procedures are performed on any subjects.

The clinical investigation will not begin until either FDA has determined that the study under the Investigational Drug Application (IND) is allowed to proceed or the Investigator has received a letter from FDA stating that the study is exempt from IND requirements.

6.5.2 Institutional Review Board Approval

The protocol, the proposed informed consent form, and all forms of participant information related to the study (e.g. advertisements used to recruit participants) will be reviewed and approved by the UAB IRB. Prior to obtaining IRB approval, the protocol must be approved by the UAB Comprehensive Cancer Center Protocol Review Committee (PRC). The initial protocol and all protocol amendments must be approved by the IRB prior to implementation.

6.5.3 Informed Consent

All participants must be provided a consent form describing the study with sufficient information for each participant to make an informed decision regarding their participation. Participants must sign the IRB-approved informed consent form prior to participation in any study specific procedure. The participant must receive a copy of the signed and dated consent document. The original signed copy of the consent document must be retained in the medical record or research file.

6.5.4 Changes in the Protocol

Once the protocol has been approved by the UAB IRB, any changes to the protocol must be documented in the form of an amendment. The amendment must be signed by the Investigator and approved by the IRB prior to implementation.

If it becomes necessary to alter the protocol to eliminate an immediate hazard to patients, an amendment may be implemented prior to IRB approval. In this circumstance, however, the Investigator must then notify the IRB in writing within five (5) working days after implementation.

6.5.5 Adverse Event Reporting

As with many IV administered agents, [⁶⁸Ga]DOTATATE could cause an allergic reaction that could potentially pose a threat to life (anaphylaxis). This has not been observed in human exposure to date. Reasonable precautions will be taken, consistent with normal radiologic and clinical facility practice. The patient will be monitored until the PET procedure is completed, and trained personnel and emergency equipment will be available per facility standards.

Qualifying Adverse Events (AEs), including Serious Adverse Events (SAEs), as defined herein, will be reported via the FDA Adverse Event Expedited Reporting System (AERS). For the [⁶⁸Ga]DOTATATE IND we will report adverse events based on the FDA final rule for IND safety reporting requirements under 21 CFR part 312 published on September 29, 2010 and implemented on March 28, 2011. This investigational study is not a BA or BE study so 21 CFR part 320 is not applicable. Adverse events will also be reported to the UAB IRB according to their requirements.

Reporting of Serious Adverse Events (SAEs) to Advanced Accelerator Applications (AAA): In addition to reporting of SAEs to the responsible IRB and Health Authority, the Principal Investigator or designee will document all SAEs that occur following receipt of [⁶⁸Ga]DOTATATE (whether or not related to study drug) to AAA. Such SAEs must be reported within 24 hours of Principal Investigator or designee becoming aware of the event. All SAE information must be reported to <https://www.adacap.com/contact-us/pharmacovigilance/>.

Additional and further requested information (follow-up or corrections to the original case) will be detailed and faxed/mailed to the same address and must include the following minimum information: The name and contact information of the reporter, the name of the study drug(s), a description of the reported SAE, with the subject identified by one or more of the following (subject initials, subject number age, sex), an investigator assessment of study drug causality, and any additional data which would aid the review and causality assessment of the case including but not limited to the date of onset, severity, the time from administration of study drug(s) to start of the event, the duration and outcome of the event, any possible etiology for the event, and the final diagnosis or syndrome, if known. If AAA receives any individually identifiable health information collected or produced in the study, AAA shall use and disclose only for the purpose of complying with applicable laws, provided that all such uses are disclosed in the IRB-approved informed consent form. AAA will use all reasonable efforts to protect the privacy and security of individually identifiable health information and will require its business partners to do so also. AAA will not contact any study subjects, unless permitted by the informed consent form.

6.5.5.1 General Definitions (from 21 CFR 312.32 (a))

Adverse Event (AE): An Adverse Event is an untoward medical occurrence associated with the use of the drug in humans, whether or not considered

drug related. For this study, the drug is [⁶⁸Ga]DOTATATE and adverse events would include any events experienced by a study participant during the Adverse Event reporting period defined in Table 1 whether or not it was considered to be related to the [⁶⁸Ga]DOTATATE. At the conclusion of the imaging study, the imaging technologist will observe the patient and also inquire if they are back to their usual state of health. If a negative answer is received, then the physician will be called to investigate this report as a possible adverse reaction.

Adverse Reaction: An Adverse Reaction is any adverse event caused by a drug. In this study, the drug is [⁶⁸Ga]DOTATATE.

Suspected adverse reaction means any adverse event for which there is a reasonable possibility that the IND drug caused the adverse event. For the purposes of IND safety reporting, “reasonable possibility” means there is evidence to suggest a causal relationship between the drug and the adverse event. A suspected adverse reaction implies a lesser degree of certainty about causality than adverse reaction, which means any adverse event caused by a drug.

An adverse event or suspected adverse reaction is considered “unexpected” if it is not listed in the investigator brochure or is not listed at the specificity or severity that has been observed; or, if an investigator brochure is not required or available, is not consistent with the risk information described in the general investigational plan or elsewhere in the current application.

An adverse event or suspected adverse reaction is considered “serious” if, in the view of either the investigator or sponsor, it results in any of the following outcomes: Death, a life-threatening adverse event, inpatient hospitalization or prolongation of existing hospitalization, a persistent or significant incapacity or substantial disruption of the ability to conduct normal life functions, or a congenital anomaly/birth defect. Important medical events that may not result in death, be life threatening, or require hospitalization may be considered serious when, based upon appropriate medical judgment, they may jeopardize the patient or subject and may require medical or surgical intervention to prevent one of the outcomes listed in this definition. Examples of such medical events include: allergic bronchospasm requiring intensive treatment in an emergency room or at home, blood dyscrasias or convulsions that do not result in inpatient hospitalization, or the development of drug dependency or drug abuse.

An adverse event or suspected adverse reaction is considered “life-threatening” if, in the view of either the investigator or sponsor, its occurrence places the patient or subject at immediate risk of death. It does not include an adverse event or suspected adverse reaction that, had it occurred in a more severe form, might have caused death.

Investigational Agent: An investigational agent is any agent held under an Investigational New Drug (IND) application. For purposes of this study, [⁶⁸Ga]DOTATATE is the investigational agent.

